#### **2.4.5.1 Analyses of hypoglycemia**

Analyses of hypoglycemia will be performed on the TEAE periods as defined in [Section 2.1.4](#). Hypoglycemia will be classified as severe hypoglycemia, documented symptomatic hypoglycemia, asymptomatic hypoglycemia, probable symptomatic hypoglycemia or relative hypoglycemia [Section 2.1.4.1](#).

The number (%) of patients with any hypoglycemia, severe hypoglycemia, and documented symptomatic hypoglycemia will be summarized respectively by treatment group during the TEAE period, as well as the incidence rate in patient years. Two types of incidence rates will be presented: the number of patients with at least 1 event per 100 patient years (calculated as the number of patients with at least 1 event / total exposure in 100 patient years), and the number of events per 100 patient-years [calculated as the total number of events / (total exposure in 100 patient-years)]. Note: here exposure (in days) is duration of TEAE period, ie, duration of IMP treatment in days +1 (Section 2.1.4).

The summary of frequency and incidence rate in patient years for severe hypoglycemia or documented symptomatic hypoglycemia will be provided as appropriate by gender (Male, Female), age group (<50, ≥50 to <65, ≥65 years), race (White, Black or African American, Asian, Other) and Metformin use at Screening (Yes, No).

A KM curve will also be provided by treatment group for the time to first severe hypoglycemia or documented symptomatic hypoglycemia during the TEAE period for the 79-week entire treatment period only.

Documented symptomatic hypoglycemia maybe presented by  $\leq 3.9$  mmol/L ( $\leq 70$  mg/dL) and  $< 3.0$  mmol/L ( $< 54$  mg/dL) respectively, as appropriate.

A listing of patients for all events reported on the dedicated e-CRF “Hypoglycemic event information” page will be provided with each category flagged (ie, severe hypoglycemia, documented symptomatic hypoglycemia, asymptomatic hypoglycemia, probable symptomatic hypoglycemia and relative hypoglycemia).

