11.4.3.2 Analyses of hypoglycemia

The number (%) of patients and rate in patient years (2 types: the number of patients with events or the total number of events per 100 patient-year) of all hypoglycemia, severe hypoglycemia, and documented symptomatic hypoglycemia will be summarized by treatment group respectively. Their pattern of occurrence over time will also be assessed, as appropriate.

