### 2.4.3.1 Extent of investigational medicinal product exposure

The extent of IMP exposure will be assessed by the duration of IMP exposure.

Duration of IMP exposure is defined as last dose date of double-blind IMP – first dose date of double-blind IMP + 1 day, regardless of unplanned intermittent discontinuations (see [Section 2.5.3](#) for calculation in case of missing or incomplete data). Duration of IMP exposure will be summarized descriptively as a quantitative variable (number of patients exposed, mean, SD, median, minimum, and maximum). In addition, duration of treatment exposure will also be summarized categorically by numbers and percentages for each of the following categories and cumulatively according to these categories:

- 1 to 28 days,
- 29 to 56 days,
- 57 to 84 days,
- 85 to 126 days,
- 127 to 182 days,

- 183 to 364 days,
- 365 to 551 days,
- >551 days.

Additionally, the cumulative duration of treatment exposure will be provided, defined as the sum of the duration of treatment exposure for all patients, and will be expressed in patient years.

Number and percentage of patients by final dose at the end of the treatment will also be presented by each treatment group.

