### ***Time to event analysis***

For time to event analysis/KM plot, time to event (eg, treatment discontinuation, rescue therapy, hypoglycemia, etc) is defined as the number of days from the date of the first administration of double-blind IMP (or the date of randomization if not exposed) to the start date of the first occurrence of the event during the 79-week double-blind treatment period.

Patients who did not experience any event during the 79-week double-blind treatment period are considered censored observations. For time to treatment discontinuation/rescue therapy, censoring date is the date of EOT. For time to severe or documented hypoglycemia, censoring date is date of EOT+1 or date of EOS, whichever is the earliest. Date of EOS will be used if date of EOT is not available. Last contact date will be used if date of EOS is not available.

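### The patient-level hypoglycemia rate keeps time after the first event in its denominator, so it runs below the first-event rate and, for common categories, tends to shrink the contrast between arms

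*SAP*

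**What the plan says.** SAP 2.4.5.1 plans two incidence rates per 100 patient-years. The patient-level rate is "calculated as the number of patients with at least 1 event / total exposure in 100 patient years". The event-count rate divides all events by the same total exposure. A note fixes the denominator: "here exposure (in days) is duration of TEAE period, ie, duration of IMP treatment in days +1". SAP 2.4.3.1 supplies the treatment duration: "Duration of IMP exposure is defined as last dose date of double-blind IMP – first dose date of double-blind IMP + 1 day". Neither section ends a patient's time at an event.

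Protocol 11.4.3.2 names the same two rates, "the number of patients with events or the total number of events per 100 patient-year", and does not define the denominator further.

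The same SAP section also plans counts and percentages: "The number (%) of patients with any hypoglycemia, severe hypoglycemia, and documented symptomatic hypoglycemia will be summarized respectively by treatment group". It adds a time-to-first-event display: "A KM curve will also be provided by treatment group for the time to first severe hypoglycemia or documented symptomatic hypoglycemia". That curve is for the 79-week period only. Its censoring rule is in SAP 2.5.4: "For time to severe or documented hypoglycemia, censoring date is date of EOT+1 or date of EOS, whichever is the earliest". SAP 2.4.5 summarizes safety for the 26-week core period and the 79-week period separately. It plans no statistical testing of safety data and allows relative risks with confidence intervals if relevant.

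**The concern.** A rate whose numerator is patients with a first event needs time at risk of a first event as its denominator. Here a patient who has an event in week 4 and stays on treatment to week 79 adds one to the numerator and about 75 further weeks to the denominator, when that patient can no longer add to the count. The arm with more hypoglycemia carries more such time, so its rate is reduced by more.

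Protocol 4.2 names hypoglycemia as a risk that may increase when the drug is added to a sulfonylurea, so readers will look at this table. The effect depends on how common the category is. *Any hypoglycemia* can take in asymptomatic readings at or below 70 mg/dL (SAP 2.1.4.1), in sulfonylurea-treated patients who self-test at least three times a week (Protocol 9.2.1.6). It is the category most likely to be common.

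**Working it through.** The documents state no hypoglycemia risk, rate or ratio, so there is no planned figure to reproduce. Event risks, true ratios and discontinuation rates below are assumptions. The rate formulas come from SAP 2.4.5.1 and 2.4.3.1. Full follow-up is taken as 79 × 7 + 1 = 554 days, so τ = 554/365.25 = 1.517 years.

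**1. Within one arm.** With x patients having an event, N patients and total exposure T, the planned rate is x/T = (x/N)/(T/N), the crude proportion divided by mean exposure. For illustration, 50 of 250 patients and 352.6 patient-years give 50/3.526 = 14.18 per 100 patient-years. By the other route, 20% divided by 352.6/250 = 1.410 years is also 14.18.

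**2. Against the first-event rate.** Each patient's total exposure is at least as long as the time to first event or end of period. The planned rate can therefore never exceed the first-event rate, and it is lower if anyone continues after an event. Protocol 10.3 asks that treatment continue whenever possible.

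**3. Between arms, constant hazards, full exposure in both.** Let p0 be the placebo risk and 2.0 the true rate ratio. Then p1 = 1 − (1 − p0)² = p0(2 − p0). The ratio of planned rates is p1/p0 = 2 − p0. Planned rates are p/τ; first-event rates are −ln(1 − p)/τ.

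| Placebo risk | Planned rates per 100 PY (placebo, sotagliflozin) | First-event rates | Planned ratio | True ratio |
|---|---|---|---|---|
| 5% | 3.3, 6.4 | 3.4, 6.8 | 1.95 | 2.00 |
| 10% | 6.6, 12.5 | 6.9, 13.9 | 1.90 | 2.00 |
| 20% | 13.2, 23.7 | 14.7, 29.4 | 1.80 | 2.00 |
| 30% | 19.8, 33.6 | 23.5, 47.0 | 1.70 | 2.00 |

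At a true ratio of 1.5, p1 = 1 − (1 − p0)^1.5. The planned ratios are 1.496 at 1% placebo risk, 1.481 at 5%, 1.462 at 10%, 1.422 at 20% and 1.381 at 30%. The share of the relative excess lost, (1.5 − planned ratio)/0.5, is about 1%, 4%, 8%, 16% and 24%.

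**4. Unequal discontinuation, constant hazards.** With event hazard λ and discontinuation hazard d, mean exposure is E = (1 − e^(−dτ))/d. Mean time at risk is A = (1 − e^(−(λ+d)τ))/(λ+d). The proportion with an event is λA, and the planned rate is λA/E. Take a 5% placebo risk (over τ, before discontinuation) and a true ratio of 1.5.

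- Discontinuation 30% placebo, 10% sotagliflozin: mean exposures are 1.276 and 1.440 years, the crude risk ratio is 1.670, and the planned ratio is 1.670 × 1.276/1.440 = 1.480.
- Arms reversed: the crude risk ratio is 1.315, and the planned ratio is 1.315 × 1.440/1.276 = 1.484.

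**5. Early events with unequal discontinuation.** All events fall in the first 8 weeks, with placebo risk 10%, true hazard ratio 1.2, and discontinuation 10% placebo and 30% sotagliflozin. The crude risk ratio is 1.173, the planned ratio is 1.324, and the ratio with time to first event in the denominator is 1.349. Both rates exceed 1.2, because the extra placebo follow-up comes when no events occur.

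**The case against.** The strongest reply is that this is one descriptive row among several. The event-count rate has a matching numerator and denominator and covers any, severe and documented symptomatic events. The Kaplan-Meier curve handles time to first event correctly for severe or documented symptomatic events. Percentages and a full event listing are also planned, and the SAP prints the formula, so nobody is misled about what was computed. No ratio of these rates is prespecified, and no test depends on them. All of this stands, and it limits the weight of the point.

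It does not close the gap. The event-count rate answers a different question, because a few patients with many episodes can drive it. The curve leaves out any hypoglycemia, the core period and the subgroups by sex, age, race and metformin use. None of those gets a first-event rate on time at risk.

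A reader might infer two stronger things. The first is that the rate merely rescales the percentage and so adds nothing. That is exact within an arm, but each arm is scaled by its own mean exposure. Step 4 shows the rate staying near 1.5 when unequal discontinuation moves the crude risk ratio to 1.670 or 1.315. The second is that the rate understates any excess on sotagliflozin. The documents fix neither event timing nor discontinuation, and step 5 shows an overstatement. If patients stop treatment at their first event, the difference largely disappears. Constant hazards are also uncertain here, because the sulfonylurea may be reduced for safety and insulin may be added as rescue.

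**Conclusion.** The point holds in a limited form. The denominator includes time after the first event, so each arm's patient-level rate is below its first-event rate whenever patients continue treatment after an event. That part needs no assumed event rate.

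The between-arm effect is conditional. Under roughly constant hazards and similar exposure, the ratio is pulled toward the crude risk ratio: for an assumed true ratio of 2.0, from 1.95 at 5% placebo risk to 1.70 at 30%. For a rare category such as severe hypoglycemia the loss is negligible. For a common category such as any hypoglycemia it is material. The documents do not support a claim that every excess would be understated, or that the rate carries no information beyond the percentage. No tested result or error rate is affected.

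**What to change.** In SAP 2.4.5.1, for the patient-level rate only, define the denominator as the sum over patients of time from first dose to the first event of that category, or to the end of the treatment-emergent period if there is no such event. Apply this separately to each category, each period and each subgroup. Keep total exposure for the event-count rate.

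The dates are already collected. SAP 2.5.4 already derives time to first event for severe or documented symptomatic hypoglycemia, so the same derivation can be extended. Protocol 11.4.3.2 leaves this denominator open, so the change does not conflict with it.

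The cost is one sentence and one extra derived variable per category. The revised rates will not be directly comparable with any other tables that use total exposure, and a footnote should say so. The change corrects the mismatch between numerator and denominator. It does not remove the distortion in step 5, where hazards vary over time and discontinuation differs, so the rates should still be read beside the Kaplan-Meier curve.

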#### **2.4.5.2 Analyses of adverse events**

##### **Generalities**

The primary focus of adverse event reporting will be on TEAEs. Pretreatment and posttreatment AEs will be described separately.

If an AE date/time of onset (occurrence, worsening, or becoming serious) is incomplete, an imputation algorithm will be used to classify the adverse event as pretreatment, treatment-emergent, or posttreatment. The algorithm for imputing date/time of onset will be conservative and will classify an AE as treatment emergent unless there is definitive information to determine it is pretreatment or posttreatment. Details on classification of AEs with missing or partial onset dates are provided in Section 2.5.3.

Adverse event incidence tables will be presented by SOC, HLG, HLT, and PT, sorted by the internationally agreed order for SOCs and alphabetic order for HLG, HLT and PT within a SOC, the number (n) and percentage (%) of patients experiencing an adverse event. Multiple occurrences of the same event in the same patient will be counted only once in the tables within a treatment phase. The denominator for computation of percentages is the safety population within each treatment group.

Sorting within tables ensures the same presentation for the set of all AEs within the observation period (pretreatment, treatment-emergent, and posttreatment). For that purpose, the table of all TEAEs presented by primary SOC and PT (sorted by the internationally agreed SOC order and decreasing frequency of PTs within SOCs in the sotagliflozin 400 mg group) will define the presentation order for all other similar tables unless otherwise specified. In case of equal frequency regarding PTs, alphabetical order will be used.

### **Analysis of all TEAEs**

The following TEAE summaries will be generated during the 26-week core and the 79-week entire treatment periods respectively in the safety population.

- Overview of TEAEs, summarizing number (%) of patients with any
  - TEAE,
  - Serious TEAE,
  - TEAE leading to death,
  - TEAE leading to permanent treatment discontinuation.
- All TEAEs by primary SOC, showing number (%) of patients with at least 1 TEAE, sorted by internationally agreed order of primary SOC.
- All TEAEs by primary SOC, HLGT, HLT, and PT, showing number (%) of patients with at least 1 TEAE sorted by the SOC internationally agreed order. The other levels (HLGT, HLT, PT) will be presented in alphabetical order.
- Number (%) of patients experiencing TEAE(s) presented by PT, sorted by decreasing incidence of PT in the sotagliflozin 400mg group.
- All TEAEs by primary SOC and PT, showing the number (%) of patients with at least 1 TEAE, sorted by the internationally agreed SOC order and by decreasing incidence of PTs within each SOC in the sotagliflozin 400mg group. This sorting order will be applied to all other similar tables, unless otherwise specified.
- All TEAEs regardless of relationship and related to IMP by primary SOC, HLGT, HLT and PT, showing the number (%) of patients with at least 1 TEAE, sorted by the internationally agreed SOC order. The other levels (HLGT, HLT, PT) will be presented in alphabetical order.
- All TEAEs by maximal severity, presented by primary SOC and PT, showing the number (%) of patients with at least 1 TEAE by severity (ie, mild, moderate, or severe), sorted by the sorting order defined above.
- Common TEAEs (PTs with an incidence  $\geq 2\%$  in any treatment group) by primary SOC, HLGT, HLT, and PT, sorted by internationally agreed order of SOCs. The other levels (HLGT, HLT, PT) will be presented in alphabetic order.

- Common TEAEs (PTs with an incidence  $\geq 2\%$  in any treatment group) will be provided as appropriate by primary SOC, and PT and by demographic factors including gender (Male, Female), age group (<50,  $\geq 50$  to <65,  $\geq 65$  years of age), race (White, Black or African American, Asian, other), baseline SBP category (<130 mmHg,  $\geq 130$  mmHg), Metformin use at Screening (Yes, No), and baseline eGFR category ( $\geq 30$  to <60 mL/min/1.73m^2 [Moderate decrease in GFR],  $\geq 60$  to <90 mL/min/1.73m^2 [Mild decrease in GFR], and  $\geq 90$  mL/min/1.73m^2 [Normal]). SOC will be sorted by internationally agreed order and the PT by decreasing incidence within each SOC in the sotagliflozin 400 mg group, as described above.
- TEAEs (PTs with an incidence  $\geq 5\%$  in any treatment group) by primary SOC, HLGT, HLT, and PT, sorted by internationally agreed order of SOCs. The other levels (HLGT, HLT, PT) will be presented in alphabetic order.

#### **Analysis of all treatment emergent SAE(s)**

- All treatment-emergent SAEs by primary SOC, HLGT, HLT, and PT, showing the number (%) of patients with at least 1 serious TEAE, sorted by the internationally agreed SOC order. The other levels (HLGT, HLT, PT) will be presented in alphabetical order
- All treatment-emergent SAEs regardless of relationship and related to IMP, by primary SOC, HLGT, HLT, and PT, showing the number (%) of patients with at least 1 treatment-emergent SAE, sorted by the internationally agreed SOC order. The other levels (HLGT, HLT, PT) will be presented in alphabetical order.

#### **Analysis of all TEAE(s) leading to treatment discontinuation**

- All TEAE leading to treatment discontinuation, by primary SOC, HLGT, HLT, and PT, showing the number (%) of patients sorted by the internationally agreed SOC order. The other levels (HLGT, HLT, PT) will be presented in alphabetical order.

#### **Analysis of AESI**

The summaries of AESI will be presented for the 79-week entire treatment period only in the safety population.

Pregnancy and overdose will be included in overall AE summaries if any are reported. ALT increase  $>3$  x ULN is included in laboratory PCSA summary if any.

The number (%) of patients with an AESI will be summarized by PT and by treatment group during the 79-week entire treatment period only. Corresponding listings will be provided as appropriately.

#### **Analysis of EOSI**

The summaries of EOSI will be presented for the 79-week entire treatment period only in the safety population.

*CV events, bone fracture and DKA*

For EOSIs that are adjudicated (ie, deaths, myocardial infarction, stroke, and unstable angina requiring hospitalization, heart failure requiring hospitalization, bone fracture, and diabetic ketoacidosis), the number (%) of patients with an EOSI positively adjudicated by CEC will be summarized by treatment group. All EOSIs sent for adjudication and/or reported by the investigators in the specific AE forms will be listed along with the adjudication outcome.

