5.2 SECONDARY

- To compare sotagliflozin 400 mg versus placebo for:
 - Change from Baseline in FPG at Week 26
 - Change from Baseline in body weight at Week 26
 - Change from Baseline in SBP at Week 12 for patients with Baseline SBP \geq 130 mmHg
 - Change from Baseline in SBP at Week 12 for all patients
 - Proportion of patients with HbA1c $<$ 6.5%, $<$ 7.0% at Week 26
- To evaluate the safety of sotagliflozin 400 mg versus placebo throughout the 79-week trial

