9.2 SAFETY ENDPOINTS

Assessments for safety include AEs, SMBG, clinical laboratory assessments, physical examination, electrocardiogram (ECG), weight, and vital signs. An independent DMC will meet on a regular basis to review accumulating clinical trial safety data.

Adjudication of all deaths, MACE/other selected CV events (MI, stroke, unstable angina leading to hospitalization, and heart failure leading to hospitalization), selected renal events, bone fracture, and DKA will be performed in a blinded manner by a CEC(s) comprised of experts. Details will be provided in the charter of the CEC(s). Further details are available in [Section 6.4](#).

Two expert committees will review all potential cases of DILIs and cases of amputation in a treatment-blinded manner to evaluate causality.

The following safety endpoints will be assessed:

- Adverse events, AEs leading to discontinuation from the IMP, adverse events of special interest (AESIs), events of special interest (EOSIs), SAEs and deaths
- Hypoglycemia (all, severe, and/or documented symptomatic hypoglycemia)
- Clinical laboratory results (including fasting lipids; see [Section 9.2.1.3](#))
- Vital signs and ECG results.

Observation period of safety endpoints

The observation period of safety data will be divided into 3 segments:

- The pre-treatment period is defined as the time between the date of the informed consent and the first dose of double-blind IMP
- The on-treatment period (TEAE period) is defined as the time from the first dose of double-blind IMP up to 10 days (1 day for hypoglycemia) after the last dose of double-blind IMP, regardless of the introduction of rescue therapy. The 10-day interval is

chosen based on the half-life of the IMP (approximately 5 times the half-life of sotagliflozin in patients with moderate renal dysfunction)

- The post-treatment period is defined as the time starting 11 days after the last dose of double-blind IMP (after the on-treatment period)

The Baseline value for safety endpoints in the safety population is the last available value (or the average of all values for creatinine or eGFR) prior to the first administration of double-blind IMP.

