10.2.2 Source data verification requirements for screen failures

For screen failure patients, the following source data must be verified: patient's identification details, the informed consent signed by the patient, the study identification (name), dates of study visits and the main reasons for screen failure.

10.3 HANDLING OF PATIENT TEMPORARY OR PERMANENT TREATMENT DISCONTINUATION AND OF PATIENT STUDY DISCONTINUATION

The IMP should be continued whenever possible. In case the IMP is stopped, it should be determined whether the stop can be made temporarily; permanent IMP discontinuation should be a last resort. Any IMP discontinuation should be fully documented in the e-CRF. In any case, the patient should remain in the study and followed for the remainder of the study duration to collect vital safety status and endpoint data.

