#### *Observation period*

The observation period will be divided into 4 epochs:

- The **screening** epoch is defined as the time from the signed informed consent date up to the first administration of the double-blind IMP.
- The **treatment** epoch is defined as the time from the first administration of the double-blind IMP to the last administration of the double-blind IMP. This epoch includes the 26-week double-blind core treatment period and the 53-week double-blind extension treatment period. The core treatment period is the time from the first administration of double-blind IMP to the last administration of double-blind IMP on or before Visit 9/Week 26 (or Day 182 if Visit 9/Week 26 date is missing).

- The **residual treatment** epoch is defined as the time from the last administration of the double-blind IMP up to 10 days (1 day for hypoglycemia) after the last administration of double-blind IMP.

The treatment-emergent adverse event (TEAE) period will include both treatment and residual treatment epochs (See the TEAE period for the core treatment period in [Section 2.5.4](#)).

- The **posttreatment** epoch is defined as the period of time starting the day after the end of the TEAE period up to the last protocol-planned visit or the resolution/stabilization of all serious adverse events (SAE), adverse events of special interest (AESI) and events of special interest (EOSI), whichever is later.

The on-study observation period is defined as the time from start of double-blind treatment until the end of the study (defined as the last scheduled visit for those who completed the study and the date collected on e-CRF page “Completion of End of Study/Follow-up” for those who did not complete the study).

The post-study observation period is defined as the time from the day after the end of the study until the resolution/stabilization of all SAE, AESI and EOSI if applicable.

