### **2.4.5 Analyses of safety data**

The summary of safety results will be presented by treatment group.

Safety endpoints are presented in [Section 2.1.4](#). The summary of safety results will be presented by treatment group. The safety data will be summarized for the 26-week core treatment period and the 79-week entire treatment period separately, unless otherwise specified.

The “observation period” defined in [Section 2.1.4](#) is applicable in all safety analyses for the classification of AEs, determination of treatment-emergent PCSA values and the last on-treatment value for the laboratory, vital sign and ECG.

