#### **Analysis of Amputation**

The number (%) of patients with amputation will be summarized by treatment group and by PT and LLT during the study (ie, regardless of on- or post-treatment). Amputation is a procedure recorded in e-CRF “Other Procedures related to Amputation”. Patients who had a procedure related to amputation will be listed.

The number (%) of patients with an “AE leading to an amputation” will be summarized by treatment group and by PT. The “AE leading to an amputation” is determined by the AE identifier recorded in e-CRF “Other Procedures related to Amputation” when “AE correction” is chosen as the reason for the amputation procedure.

In addition, the number (%) of patients with an “AE potentially leading to an amputation” will be summarized by treatment group and by PT (as identified in [Table 3](#) in [Section 2.1.4.2](#); these PTs in [Table 3](#) were requested by the European Medicines Agency/ Pharmacovigilance Risk Assessment Committee[EMA/PRAC] Assessment Report 9 February 2017). Associated list will be provided as well, with patients who had an amputation procedure flagged. “AE potentially leading to an amputation” represents the condition that may potentially lead to the amputation procedure, but not in all cases an amputation has occurred (as per the EMA/PRAC request).

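### By-arm summaries of events of special interest end about 10 days after last dose, and no planned table counts the main adjudicated, renal and malignancy events by arm over the whole study

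*SAP*

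**What the plan says.** - **EOSI summaries.** SAP 2.4.5.2, Analysis of EOSI: "The summaries of EOSI will be presented for the 79-week entire treatment period only in the safety population".
- **Default periods.** SAP 2.4.5: "The safety data will be summarized for the 26-week core treatment period and the 79-week entire treatment period separately, unless otherwise specified". The same section says that the observation period of SAP 2.1.4 "is applicable in all safety analyses for the classification of AEs".
- **Treatment epoch.** SAP 2.1.4 defines it as "the time from the first administration of the double-blind IMP to the last administration of the double-blind IMP". The treatment-emergent (TEAE) period adds a residual epoch of 10 days, or 1 day for hypoglycemia.
- **Reason for the 10 days.** Protocol 9.2: "The 10-day interval is" based on half-life, at roughly five half-lives in moderate renal dysfunction.
- **After stopping drug.** Protocol 10.3: "the patient should remain in the study and followed for the remainder of the study duration to collect vital safety status and endpoint data". Protocol 9.2.1.2 and 10.4.2 continue safety collection to the patient's scheduled study end.
- **Objective.** Protocol 5.2: "To evaluate the safety of sotagliflozin 400 mg versus placebo throughout the 79-week trial".
- **Where the SAP goes past the treatment window.** SAP 2.4.5.3 counts deaths on-study, on-treatment and post-study. SAP 2.4.5.2 counts amputation procedures "during the study (ie, regardless of on- or post-treatment". SAP 2.1.4 already defines an on-study observation period, from start of double-blind treatment to end of study.

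**The concern.** A window built on half-life suits events that follow drug exposure closely. It is a less obvious choice for malignancy, fracture, cardiovascular events and progression of renal disease. The renal definitions in SAP Table 3 show the mismatch: unless the endpoint committee adjudicates the event positively, an eGFR criterion needs confirmation over at least 30 days and dialysis must last at least 90 days. Both exceed 10 days, and the SAP does not say whether onset or confirmation date decides inclusion.

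The trial keeps patients who stop drug under follow-up, but the by-arm EOSI counts do not use that follow-up. These events are likely to be few, so a handful could alter how the arms compare. If stopping differs between arms, the two arms also lose different amounts of follow-up from the count.

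**Working it through.** The plan states no figure for EOSIs, so there is none to reproduce. The check has three steps.

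**1. What window applies.** The EOSI sentence does not mention last dose, 10 days or treatment-emergent. Set beside the default of separate 26-week and 79-week summaries, its restriction mainly drops the 26-week table. The cut-off follows from SAP 2.1.4 (the treatment epoch, containing the core and extension periods, ends at last dose; the TEAE period adds 10 days) and from the SAP 2.4.5 rule. SAP 2.4.5.1 pairs the same 79-week label with the TEAE period for the hypoglycemia curve. The natural reading is therefore first dose to last dose + 10 days (1 day for severe hypoglycemia, itself an EOSI).

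**2. Where a later event would appear.**

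| SAP output | Covers time after last dose + 10 days? | By arm? | Grouped or adjudicated? |
|---|---|---|---|
| EOSI summaries (2.4.5.2) | No | Yes | Yes |
| Posttreatment AE table (2.4.5.2) | That time only | Yes, by the general rule in 2.4.5 | No: individual preferred terms |
| Listings of adjudicated and renal events (2.4.5.2) | No time limit stated | Patient level, no counts | Outcome shown where applicable |
| Death counts (2.4.5.3) | Yes | Yes | Not by cause |
| Amputation procedures (2.4.5.2) | Yes | Yes | Procedure count |

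The EOSI and posttreatment tables cannot be added together, because one patient may be in both and the units differ (EOSI group or adjudicated event against single preferred term). So no planned output gives the whole-study number of patients per arm with an adjudicated MI, stroke, unstable angina, heart failure event or fracture, a renal event, or a grouped malignancy of special interest.

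**3. How much follow-up lies outside.** Inputs: Week 79 = Day 551 (Protocol 1.2); 10-day residual (SAP 2.1.4); 250 patients per arm (Protocol 11.1). Assumed, because the documents give no values: the share *s* stopping early, the timing of stopping, full follow-up to Day 551, and the event rate.

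- One patient stopping on Day *t* leaves 551 − (*t* + 10) days outside: Day 28, 513 days (93%); Day 84, 457 (83%); Day 182, 359 (65%); Day 364, 177 (32%).
- Stop days uniform over 1 to 551: mean days outside = (540 × 541 / 2) / 551 = 146,070 / 551 = 265.1, or 48.1% of 551. Share of planned time outside = *s* × 0.481.
- All stopping on Day 84: share = *s* × 457/551 = *s* × 0.829.
- Planned time per arm = 250 × 551 / 365.25 = 377.1 patient-years. At 1 event per 100 patient-years, 3.8 events are expected per arm.

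| *s* | Patient-years outside per arm (uniform) | Share (uniform) | Share (all on Day 84) | Expected events outside per arm (uniform) |
|---|---|---|---|---|
| 5% | 9.1 | 2.4% | 4.1% | 0.09 |
| 15% | 27.2 | 7.2% | 12.4% | 0.27 |
| 25% | 45.4 | 12.0% | 20.7% | 0.45 |

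With 25% all stopping on Day 84, 78.2 patient-years fall outside, or 0.78 events at the same rate. At 4 events per 100 patient-years and 25% uniform stopping, it is 1.8 of 15.1.

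**The case against.** The strongest defense is that this is a deliberate and ordinary choice. Both documents declare a focus on treatment-emergent events (Protocol 11.4.3.1, SAP 2.4.5.2), and safety is descriptive with no testing planned (SAP 2.4.5), so neither type I error nor power is touched. Later events are reported in the outputs set out above. Off drug, patients may receive other treatments, so an on-study count can dilute a drug-related harm. Nor would it be a strictly randomized comparison, because it starts at first dose in a population analyzed by treatment received (SAP 2.3.2). Some patients who stop will agree only to telephone contact (Protocol 6.1.2) or will leave the study (Protocol 10.3.5), so less time may be recoverable than the calculation assumes.

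Most of this stands, and it is why the on-study count should supplement the existing table and not replace it. It does not supply the missing count: the table of single preferred terms and the patient listings cannot be turned into by-arm numbers of patients with an adjudicated or grouped EOSI without an analysis the SAP does not specify.

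**Conclusion.** The point holds as a gap in completeness, with possible bias in a by-arm count if stopping differs between arms. It rests on the natural reading of SAP 2.1.4 and 2.4.5. Its size depends on assumed inputs: about 2.4% to 12.0% of planned patient-time for 5% to 25% uniform stopping with full follow-up, and under one event per arm at 1 event per 100 patient-years.

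Four stronger readings are tempting, and the documents do not support them:

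- **That later events vanish, or that the safety objective goes unanswered.** They are tabulated, listed or counted as deaths elsewhere, and the objective is addressed by the whole safety section.
- **That the quoted sentence itself sets the cut-off.** It does not; the cut-off is inferred from other sections.
- **That patients often stop because of the event, so the truncation is known to be informative.** No figure or statement in the documents shows this.
- **That amputation proves EOSIs are handled inconsistently.** The on-study wording covers the procedure count. The EOSI is the adverse event leading to amputation, and its paragraph has no such wording.

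Malignancies are also not adjudicated (SAP Table 3), so for them the missing item is the grouped count only.

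**What to change.** In SAP 2.4.5.2, Analysis of EOSI:

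1. State that the existing EOSI table uses the TEAE window, and whether onset or confirmation date decides inclusion of a renal event.
2. Add one supplementary by-arm summary over the on-study observation period of SAP 2.1.4, regardless of drug discontinuation, for adjudicated MI, stroke, unstable angina, heart failure and fracture, for renal events, and for grouped malignancies of special interest.
3. Keep the treatment-period table and show both, since off-drug time may dilute drug-related effects.
4. Complete the adverse event row of SAP Appendix C, which still marks EOSI as awaiting an update.

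The cost is SAP wording and one extra descriptive table. The plan already provides for collecting and, where applicable, adjudicating these events, so no new visits, patients or data are needed.
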